6.1 Demographic and baseline variables

The demographic and baseline variables of the ALASCCA trial are listed in Table 7.

Table 7. Demographic and baseline variables in the ALASCCA trial

Variable	Туре	Range/categories	Unit of measureme nt
Age at screening visit 2	Continuous	18-80	Years (truncated to integer)
Sex	Dichotomous	Female/Male	-
Country	Categorical	Sweden/Norway/Denmark/Finland	
Date of randomization	Date	2016-07-07 – 2021-07-19	YYYY-MM- DD
Date of CRC diagnosis	Date	-	YYYY-MM- DD
Date of CRC surgery	Date	-	YYYY-MM- DD
Mutation	Categorical	- PIK3CA (exon 9 and/or 20) - PIK3CA (not exon 9 or 20), PIK3R1 or PTEN	
BMI	Continuous		kg/m²
Platelet count	Continuous	≥0	x10^9/L
CEA	Continuous	≥0	μg/L

Variable	Туре	Range/categories	Unit of
			measureme nt
ASA Score	Categorical	1-5	-
Tumor location	Dichotomous	Colon/Rectum	
Tumor location	Categorical	Caecum/Ascendens/Flexura	
in colon cancer	Catogorical	hepatica/Transversum/Flexura	
in colon cancol		lienalis/Descendens/Sigmoideum	
Height from anal	Continuous	≥0	cm
verge (rectal			
cancer)			
Colon tumor	Dichotomous	II, III	_
stage		.,	
Rectal tumor	Categorical	I, II, III	_
stage		, .,	
Neoadjuvant RT	Dichotomous	Yes/No	_
Neoadjuvant	Dichotomous	Yes/No	_
chemotherapy	Dionotomodo	1 65/116	
Neoadjuvant	Dichotomous	Yes/No	_
CRT	Bioriotomodo	135/113	
Type of	Categorical	RT only/CRT/RT+Chemo/CRT+Chemo/Chemo	_
neoadjuvant	Outogorioui	only/No neoadjuvant treatment	
treatment		only/No neodajavani treatment	
Start of	Date		YYYY-MM-
neoadjuvant RT	Date		DD
Start of	Date		YYYY-MM-
neoadjuvant	Date		DD
chemo in CRT			
Start of	Date		YYYY-MM-
neoadjuvant	Date		DD
chemo			
Neoadjuvant RT	Categorical	5 Gy/2 Gy/1.8 Gy/Other	_
dose	Catogorica		
Neoadjuvant RT	Categorical	5 fractions/25 fractions/28 fractions	-
fraction		0 1130110/10/20 1130110/10/20 1130110/10	
5-FU in	Dichotomous	Yes/No	_
neoadjuvant			
CRT			
Capecitabin in	Dichotomous	Yes/No	-
neoadjuvant			
CRT			
Other	Dichotomous	Yes/No	-
chemotherapy in			
neoadjuvant			
CRT			
Specification of	Text	-	-
other			
chemotherapy in			
neoadjuvant			
CRT			
5-FU in adjuvant	Dichotomous	Yes/No	-
chemo			
Capecitabin in	Dichotomous	Yes/No	-
neoadjuvant			
chemo			
Oxaliplatin in	Dichotomous	Yes/No	-
neoadjuvant			
chemo			

Variable	Туре	Range/categories	Unit of measureme
			nt
Other neoadjuvant chemotherapy	Dichotomous	Yes/No	-
Specification of other	Text	-	-
neoadjuvant chemotherapy			
Surgery	Dichotomous	Elective/emergency	-
Type of surgery	Categorical	Ileocecal resection/Right-sided hemicolectomy/Transversum resection/Left- sided hemicolectomy/Sigmoideum resection/Total colectomy/Anterior resection/Rectum amputation/Hartmann's procedure	-
pTNM stage	Categorical	I, II, III, IV	-
Tumor differentiation	Dichotomous	Low grade/High grade	-
MSI	Categorical	MSI-high/MSI-low/Uncertain	
BRAF-mutation	Categorical	Yes/No/Uncertain	
KRAS-mutation	Categorical	Yes/No/Uncertain	
NRAS-mutation	Categorical	Yes/No/Uncertain	
Adjuvant chemotherapy	Dichotomous	Yes/No	-
Type of adjuvant treatment	Categorical	RT only/CRT/RT+Chemo/CRT+Chemo/Chemo only/No adjuvant treatment	-
Start of adjuvant RT	Date		YYYY-MM- DD
Start of adjuvant chemo in CRT	Date		YYYY-MM- DD
Start of adjuvant chemo	Date		YYYY-MM- DD
Adjuvant RT dose	Categorical	5 Gy/2 Gy/1.8 Gy/Other	-
Adjuvant RT fraction	Categorical	5 fractions/25 fractions/28 fractions	-
5-FU in adjuvant CRT	Dichotomous	Yes/No	-
Capecitabin in adjuvant CRT	Dichotomous	Yes/No	-
Other chemotherapy in adjuvant CRT	Dichotomous	Yes/No	-
Specification of other chemotherapy in	Text	-	-
adjuvant CRT 5-FU in adjuvant chemo	Dichotomous	Yes/No	-
Capecitabin in adjuvant chemo	Dichotomous	Yes/No	-
Oxaliplatin in adjuvant chemo	Dichotomous	Yes/No	-
Other adjuvant chemotherapy	Dichotomous	Yes/No	-

Variable	Туре	Range/categories	Unit of measureme nt
Specification of other adjuvant	Text	-	-
chemotherapy			

6.2 Derived variables

6.2.1 Endpoint variables

For the primary endpoint TTR assessed at 3 years, subjects will be censored at the date for which they are last known to be free of CRC recurrence. Subjects who are alive and free of CRC recurrence at 3 years plus 21 days (allowing for the 21-day visit-window) will be censored at that time-point. Subjects who have withdrawn their written informed consent during the trial will be censored at the withdrawal date. Subjects who have relocated, and where information on endpoints is not collectable, will be censored at date of relocation. Subjects who have died will be censored at the date of death. For subjects experiencing CRC recurrence, TTR will be calculated as the number of days from randomization until date of CT/MRI, or EoS date if the aforementioned date is missing, or recurrence date collected separately from sites if recurrence has not been entered into the eCRF (see Section 4.9 for details on data collection). For subjects not experiencing CRC recurrence, TTR will be calculated as the number of days from randomization until date of censoring (see above). The TTR event indicator will be defined as 1 for subjects who have experienced CRC recurrence with a CT/MRI/EoS/recurrence date within 3 years plus 21 days from randomization, and 0 for those that have not. The time variable will be named ttr3y, and the event indicator will be named rec status 3y.

TTR will also be assessed at 5 years (see Section 8.3). The variables *ttr5y* and *rec_status_5y* will be created similarly as described above, with censoring at 5 years plus 30 days.

For the secondary endpoint DFS assessed at 3 years, subjects who are free of CRC recurrence, second primary CRC, other cancer, or death from any cause will be censored at the date for which they are last known to be free of such events. Subjects who are free of the above events at 3 years plus 21 days (allowing for the 21-day visit-window) will be censored at that time-point. DFS will be calculated as the number of days from randomization until recurrence date (see definition in the above paragraph), EoS date, death date or date of other cancer collected separately from sites (see Section 4.9), or the date of censoring (see above). The DFS event indicator will be defined as 1 for subjects who have a DFS event within 3 years plus 21 days from randomization, where DFS events are defined as:

- Having EoS reasons CRC recurrence or death, or
- Having EoS reasons "other medical reason" or "other reason", with other cancer or second primary CRC specified as reason, or
- Having a recurrence/other cancer/death collected separately from sites (see Section 4.9),

and 0 for subjects who have not reached any of the above endpoints. The time variable will be named *dfs3y*, and the event indicator will be named *dfs_status_3y*.

For the secondary endpoint OS assessed at 5 years, subjects who have not died will be censored at the date for which they are last known to be alive. Subjects who are alive at 5 years plus 30 days (allowing for the 30-day visit-window for visit 16) will be censored at that

time-point. For subjects who have died within 5 years plus 30 days from randomization, OS will be calculated as the number of days from randomization until one of the following:

- EoS date, where "Death" is entered as reason for EoS, or
- death date entered at Visit 16, or,
- death date collected separately from sites (see Section 4.9),

and the OS event variable will be defined as 1 for such subjects. For other subjects, the OS event variable will be defined as 0, and OS will be calculated as the number of days from randomization until date of censoring (see above). The time variable will be named *os5y*, and the event indicator will be named *os_status_5y*.

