##### Secondary clinical efficacy assessments

OS will be reviewed during the study. In case the patient dies during the study the cause of death will be recorded.

Time until relapse will also be documented.

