### 10.13.2 Endpoints

#### 10.13.2.1 Primary Endpoint

Primary endpoint TTR at 3 years will be analyzed in patients with tumors harboring *PIK3CA* mutations in exon 9 and 20.

TTR is defined as time from randomization to occurrence of any of the following; loco-regional recurrence, distant metastases or death from colorectal cancer.

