### 10.13.3 Analysis of efficacy

The primary efficacy variable is TTR. Subjects who have not experienced loco-regional recurrence, distant metastases or death from colorectal cancer at time of 3- and 5- years will be censored at the time of the latest assessment. The log-rank test will be applied to test for difference in TTR between the treatment groups.

Kaplan-Meier estimates will be used for the estimation of median times to treatment failure and their confidence intervals. Secondary endpoints will be assessed using the log-rank test or

a Cox regression model, with time to treatment failure (relapse or death) as response variable and treatment group as factor.

All secondary variables will be presented descriptively with point estimate and 95% confidence intervals.

The data from the observation group will only be presented descriptively.

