4.3 Endpoints

TTR is defined as time from randomization to occurrence of any of the following: locoregional recurrence, distant metastases, or death from CRC.

DFS is defined as time from randomization to occurrence of any of the following events: loco-regional recurrence, distant metastases, second primary CRC, second primary other cancer, death from any cause, whichever comes first.

OS is defined as time from randomization to death from any cause.

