4.9 Data collection

Data collection is performed partly through the eCRF, partly through the Swedish Colorectal Cancer Registry (SCRCR) and other Swedish national registries (for Swedish subjects), and partly through separate data collections directly from trial sites (subjects in other Nordic countries). Baseline characteristics that are collected from the SCRCR for Swedish subjects are collected separately from each site for the Nordic countries outside of Sweden. Table 5 contains information on data sources for subjects in Sweden and other Nordic countries. Each data source is described in the below subsections (4.9.1, 4.9.2, 4.9.3, 4.9.4, and 4.9.6). Note that some variables are collected from several data sources, e.g. the pathological tumor-node-metastasis (pTNM) stage and cancer location. For such variables, data from the eCRF will be preferred, with the exception of data from the Department of Medical Epidemiology and Biostatistics (MEB) (see subsection 4.9.6 for details), since the eCRF is regularly monitored (see Section 4.10), but data from other sources can be used if there are data missing from the eCRF.

Table 5. Data sources for the ALASCCA clinical trial, for randomized subjects.

Variable	Sweden	Denmark, Finland, Norway
- Inclusion and exclusion criteria	eCRF	eCRF
- Mutation type (blinded) (PIK3CA (exon		
9/20) or PTEN/PIK3R1/PIK3CA (other		
exons))		
- Randomized group		
- Age at screening visit 2		
- Date of surgery		
- Sex		
- pTNM stage		
 Cancer location (colon/rectum) 		
- Compliance		
 Concomitant medication 		
- CT/MRI at 12 and 36 months		
- AEs		
Endpoint variables assessed at 3 years for	eCRF	eCRF
ubjects reaching a study endpoint or		
ompleting 3 years in the trial:		
 CRC recurrence within 3 years (local and distant) 		
- Other cancer within 3 years		
- Death within 3 years		
- CEA level (if applicable)		
- Date of 3-year follow-up CT		
additional endpoint variables assessed at 3	Collected separately	Collected separately
ears for all subjects:	from sites/SCRCR	from sites
 CRC recurrence, and corresponding date 		
 Location(s) of CRC recurrence (local/liver/lung/other) 		
 Other cancer, and type of other cancer, within 3 years, and corresponding date 		
- Death within 3 years, and corresponding date		
- Date of last known to be alive		
- CEA level (if applicable)		
- Date of 3-year follow-up CT		
Endpoint variables assessed at 5 years for	eCRF	eCRF
subjects reaching who completed 3 years in		
ne trial:		

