In addition to the Cox PHM, TTR in the two treatment arms (ASA and Placebo) will be visually inspected by the cumulative incidence function (CIF) using Aalen-Johansen estimates, including 95% CIs, from time of randomization until three years of follow-up. Death will be considered a competing event. The 1- and 3-year Aalen-Johansen estimates of cumulative incidence of CRC recurrence in each arm, along with 95 % CIs, will also be presented. Kaplan-Meier (KM) curves estimating the net proportion of CRC recurrence, including 95% CIs, from time of randomization until three years of follow-up will be included as a supplementary figure.

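### The SAP's coding of time to recurrence censors colorectal cancer deaths without a recorded recurrence, although both documents define such deaths as events

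*SAP*

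**What the plan says.** **Definition.** SAP 4.3 states: "TTR is defined as time from randomization to occurrence of any of the following: locoregional recurrence, distant metastases, or death from CRC". Protocol 10.13.2.1 lists the same components: "loco-regional recurrence, distant metastases or death from colorectal cancer". The censoring rule in Protocol 10.13.3 agrees, because it applies only to "Subjects who have not experienced loco-regional recurrence, distant metastases or death from colorectal cancer". The synopsis (Statistical methods) has the same rule.

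**Coding.** SAP 6.2.1 builds the variables that are analysed. On deaths it says: "Subjects who have died will be censored at the date of death". On the indicator it says: "The TTR event indicator will be defined as 1 for subjects who have experienced CRC recurrence", with a qualifying date inside the 3-year window, and 0 otherwise. Subjects without recurrence receive a censoring time. The 5-year variables are built in the same way.

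**Analysis.** SAP Table 9 uses ttr3y and rec_status_3y for the primary endpoint and for secondary endpoint 2. For the cumulative incidence curves, SAP 8.1 adds: "Death will be considered a competing event", with no split by cause.

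**Data.** Protocol 10.8.4 says: "In case the patient dies during the study the cause of death will be recorded". SAP Table 5 lists "Death within 3 years, and corresponding date" but not the cause, and 6.2.1 does not use cause.

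**The concern.** The primary endpoint has two incompatible definitions in current text. A programmer who follows 6.2.1 exactly cannot produce the endpoint defined in 4.3 and in the protocol. The subjects affected are those who die of CRC with no recurrence recorded in any source. If recurrence was recorded before death, the event is already counted at the recurrence date.

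The primary event count, hazard ratio, confidence interval and p-value all depend on which section is followed. If the conflict is noticed only after unblinding, the choice could be influenced by the results. Secondary endpoint 2 and every exploratory TTR analysis, including those at 5 years, use indicators built by the same rule. DFS and OS are not affected, because they count every death.

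**Working it through.** **1. Trace one subject.** Take a subject with no recorded recurrence who dies of CRC within 3 years.

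| Source | Status of that subject |
|---|---|
| Protocol 10.13.2.1 and SAP 4.3 (definition) | TTR event |
| Protocol 10.13.3 and synopsis (censoring rule) | Not censored, because a listed event has occurred |
| SAP 6.2.1 (indicator) | rec_status_3y = 0 |
| SAP 6.2.1 (time) | Censored at date of death |
| SAP 8.1 (Cox model) | Censored |
| SAP 8.1 (cumulative incidence) | Competing event |

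No section codes this subject as an event. The end-of-study reasons in SAP 4.8 list death and CRC recurrence separately, so a subject can leave with death as the only reason.

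**2. Reproduce the design.** Inputs from SAP 4.5.2 and Protocol 10.13.7: placebo 3-year rate 18%, RR 0.38, two-sided alpha 0.05, power 80%, 10% drop-out, two-sample test for proportions, 135 per arm without and 150 with drop-out.

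- ASA rate: 0.38 × 0.18 = 0.0684. Mean rate: (0.18 + 0.0684)/2 = 0.1242.
- n per arm = [1.96·√(2·0.1242·0.8758) + 0.842·√(0.18·0.82 + 0.0684·0.9316)]² / (0.18 − 0.0684)² = 135.9, so 136. With drop-out, 136/0.9 gives 152. The plan's 135 and 150 are reproduced closely.
- Power at 135 per arm = Φ[(0.1116 − 1.96·0.04014)/0.03956] = 79.7%.
- Expected events: 135 × 0.18 = 24.3 (placebo) and 135 × 0.0684 = 9.2 (ASA), 33.5 in total.
- Implied HR: ln(1 − 0.0684)/ln(1 − 0.18) = 0.357. Schoenfeld power = Φ(½·√33.5·|ln 0.357| − 1.96) = 84.7%.

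**3. Effect of censoring a share of the events.** The documents do not say how many events would be CRC deaths without recorded recurrence, so a share s is assumed, equal in both arms. Rates become 0.18(1 − s) and 0.0684(1 − s), and events become 33.5(1 − s).

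| Assumed share s | Events lost | Events left | Power, two proportions | Power, Schoenfeld |
|---|---|---|---|---|
| 0 | 0 | 33.5 | 79.7% | 84.7% |
| 1% | 0.3 | 33.2 | 79.3% | 84.3% |
| 2.98% (one event) | 1.0 | 32.5 | 78.3% | 83.6% |
| 5% | 1.7 | 31.9 | 77.3% | 82.8% |
| 10% | 3.4 | 30.2 | 74.8% | 80.8% |

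One lost event is 1/33.5, about 3% of the information. It costs about 1.4 points of power on the two-proportion basis and 1.1 on the Schoenfeld basis.

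**4. Unequal losses.** If two events are lost in the placebo arm only, the expected RR moves from 0.38 to (9.234)/(24.3 − 2) = 0.41. If two are lost in the ASA arm only, it moves to (9.234 − 2)/24.3 = 0.30. The shift can go either way, so no direction of bias follows.

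**5. Condition on steps 3 and 4.** These losses are real only if the planned 18% includes CRC deaths without recurrence. SAP 4.5.2 calls it a cumulative incidence of recurrence. If it is recurrence only, no planned event is lost.

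**The case against.** The strongest case on the other side has four parts.

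- **Few subjects are affected.** Entry requires radical surgery and no distant metastases, so a CRC death would normally follow a recurrence. SAP Table 5 collects recurrence and its date for all subjects, and 6.2.1 accepts a date supplied by the site when the eCRF has none. The count could be zero. This stands as a limit on size. It does not remove the conflict, because the coding needs a recorded, dated recurrence and not one inferred from the cause of death. If every CRC death did carry such a record, the third component of the definition would be redundant.
- **Recurrence-only coding may be intended.** The SAP revision table says version 1.1 clarified censoring due to death, and the sample-size text and figure labels speak of recurrence. That is plausible, but SAP 4.3 in the same version still includes CRC death, so one of the sections must change.
- **The power figures rest on assumptions.** This is correct: the 1% to 10% range has no source in the documents, and the equal share across arms is assumed. The figures show scale only.
- **Cause of death may be available.** Protocol 10.8.4 says it is recorded, and every death is a serious adverse event reported with a diagnosis. This makes the correction cheap, but 6.2.1 still does not use the information.

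**Conclusion.** The concern holds, with high confidence in the contradiction itself. Following SAP 6.2.1 and 8.1 as written yields a primary endpoint other than the one defined in SAP 4.3 and the protocol. It must be corrected because a primary endpoint needs a single definition, not because a loss of power has been shown.

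The practical size is unknown and probably small: on the assumed range, up to about 3 of 33.5 planned events and at most about 5 points of two-proportion power (79.7% to 74.8%). It is zero on the planning assumptions if the 18% counts recurrence alone.

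**What to change.** Choose one definition before unblinding and apply it throughout.

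**Option 1: keep the stated definition.** In SAP 6.2.1, set the TTR indicator to 1 at the date of death for a CRC death without earlier recurrence, and censor only deaths from other causes. Do the same for the 5-year variables. In SAP 8.1, define the competing event as death not due to CRC. Add cause of death to Table 5, classified blind to arm by a written rule. Adjust the figure labels that refer to recurrence only.

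**Option 2: adopt recurrence only.** Remove death from CRC from the TTR definition in SAP 4.3 and Protocol 10.13.2.1, and from the censoring rules in Protocol 10.13.3 and the synopsis. State the change openly.

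Under either option, report the number of CRC deaths without recorded recurrence in each arm.

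**Cost.** Option 1 is a change of SAP wording and labels. It needs a new form field only if the eCRF does not already hold cause of death. Option 2 changes the protocol's primary endpoint after recruitment has closed and would probably need a numbered amendment with ethics and regulatory approval under Protocol 10.12.5. Neither needs new patients or visits. Option 1 is the cheaper and preserves the endpoint the protocol defines.

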6.2.2 Variables for compliance calculation

See Section 4.8.2 for the definition of overall compliance.

The number of treatment days until the last clinic visit will be calculated as days from the date of randomization (*A_randomiseringsdatum*) until the date of the last clinic visit (*V_Visitdatum* for the latest clinic visit, where clinic visits are *V_Visit* V5, V6, V7, V8, V9, V10, V11, V13, V15).

The number of dispensed pills at a certain clinic visit will be calculated as 100 times the number of unique package numbers (*S_Package_Number*) for packages that are not shredded (*R2465T32612_MAKULERAD*) or not found at the clinic (*S_Not_Found*).

The total number of dispensed pills will be calculated as the sum of the dispensed pills at each visit.

The total number of remaining pills will be calculated as the sum of the number of remaining pills for each clinic visit (S_returned_number). If the package was lost by the subject (S_Lost_Drug="True"), and S_returned_number equals 0 or "NA", the number of remaining pills for that package will be defined as 100, to not overestimate compliance.

The number of days on break will be calculated as the sum of days from $V_UppehallFromDatum$ until $V_UppehallTomDatum$, for all visits where $V_Uppehall=1$. Treatment breaks that are longer than 30 days and unrelated to adjuvant chemotherapy will be defined as non-compliant with the study protocol. Similarly, breaks that are at most 30 days of related to chemotherapy will be defined as compliant with the study protocol. Days on treatment break that are overlapping with a later registered treatment break will be subtracted.

Compliance for subjects with an EoS event after the first phone contact but before the first clinic visit will be based on the variable *V_LMIntag* for *V_Visit*=V4.

The date for which C_{LCV} (or C_{V4}) is considered valid until ($D_{LCV/V4}$) is $E_sistaintag$, dfs_event_date , $E_endofstudydtm$, or $v15_visitdatum$. The number of valid days will be calculated as the number of days from randomization ($A_randomiseringsdatum$) until $D_{LCV/V4}$, subtracting the number of days on non-allowed treatment break (see above). The number of zero-compliance days will be calculated as days from $D_{LCV/V4}$ until $E_endofstudydtm$ or 3 years from randomization, adding the number of days on non-allowed treatment break.

The compliance variable will be named *overall_compl*, and the indicator variable for compliance of at least 80% will be named *overall_compl_80*.

